## Document History

Document	Version	Summary of Changes
Original protocol	1.0	Not applicable (N/A)
New Version		
Amendment 1	2.0	
Change from an expectation that 30-50% of randomized subjects have clinically-confirmed DH to 40-50% of the randomized subjects have to have clinically-confirmed DH.
 
Modification of Exc 6b to allow a min of 11 of the anterior 12 teeth to be allowable from requirement that all 12 be evaluable.

Amendment 2		

New versions incorporate all revisions to date prior to submission to institutional review boards/ethics committees (IRBs/ECs), etc.

Amendments incorporate all revisions to date, including amendments made at the request of institutional review boards/ethics committees (IRBs/ECs), etc.

## 1 INTRODUCTION

Tooth bleaching is a widely performed procedure that aims to improve the color (increase whiteness) of teeth to provide a cosmetic benefit. The most commonly used bleaching ingredient is hydrogen peroxide (or hydrogen peroxide-releasing ingredients such as carbamide peroxide), which functions by diffusing through the tooth enamel and oxidizing chromophores within the porous matrix of enamel and the underlying dentine. This has the effect of reducing the color within teeth and making them appear whiter.

Tooth sensitivity management works on the principle of either employing potassium-based agents aiming to stabilize pulpal nerve depolarization, or dentinal tubule occlusion agents aiming to occlude patent dentinal tubules ([Pollard et al., 2023](#)). However, many dentifrices advised by dental professionals to reduce tooth sensitivity whilst patients are undergoing tooth bleaching contain potassium ions, rather than occluding agents, likely because the number of published studies in support of occluding agents are few ([Alexandrino et al., 2017](#), [Malik et al., 2016](#), [Shivaprasad et al., 2014](#)). Therefore, conclusions from these published studies are difficult to interpret with any certainty and further studies are needed to demonstrate efficacy of dentifrices for tooth sensitivity reduction whilst patients are undergoing tooth bleaching and inform on potential treatment strategies relevant to dental professionals.

NovaMin (Calcium Sodium Phosphosilicate) is an occluding agent employed in dentifrices indicated for tooth sensitivity relief that is clinically proven to provide relief ([Gendreau et al., 2011](#)) by forming a calcium rich layer in and over the surface of exposed dentine following 5 days of twice daily use ([Jones et al., 2015](#)). The efficacy of NovaMin has been shown in a number of clinical trials where patients undergoing tooth whitening treatment were excluded ([Litkowski and Greenspan, 2010](#), [Narongdej et al., 2010](#), [de Freitas et al., 2021](#)). Given that it is now common practice for many patients to undergo tooth bleaching to achieve whiter teeth, it is of interest to understand if patients can benefit from using NovaMin to provide tooth sensitivity relief whilst undergoing tooth bleaching.

The aim of this exploratory study is to investigate the efficacy of a marketed dentifrice containing 5% NovaMin to reduce tooth sensitivity during and post tooth bleaching compared to a marketed dentifrice containing 5% potassium nitrate ( $KNO_3$ ) and a marketed regular fluoride-containing dentifrice.

### 1.1 Background & Study Rationale

This is an exploratory, proof-of-principle study. The study will be a randomized, examiner-blind, single-center, controlled, three arm, parallel group proof-of-principle exploratory study to evaluate tooth sensitivity during and following at-home tooth bleaching. This study will compare the efficacy of a dentifrice containing NovaMin, a dentine tubule occluding agent to a positive control (containing 5%  $KNO_3$ ) and a standard fluoride-containing reference dentifrice.

The tooth sensitivity benefit associated with the use of NovaMin containing dentifrices (the Test product in this study) is extensive ([Gendreau et al., 2011](#), [Arantes et al., 2019](#), [Rajesh et al., 2012](#), [Neuhaus et al., 2013](#)). NovaMin is reported to function by adhering to exposed dentin surfaces, reacting with it to form a mineralized layer that is resistant to acid challenges and is mechanically strong ([Burwell et al., 2010](#)). This layer thus occludes patent dentine tubules with a hydroxyapatite-like layer ([Earl et al., 2011](#)) and thereby reducing pulpal nerve excitation by preventing the flow of dentinal fluid initiated by thermal/osmotic/tactile stimuli ([Addy, 2002](#)). However, the ability of NovaMin to reduce tooth sensitivity whilst patients are

Property of Haleon- Confidential

May not be used, divulged, published or otherwise disclosed without the consent of Haleon

undergoing tooth bleaching is less extensively reported in the literature. In one study on the effect of a dentifrice containing a bioactive glass similar to NovaMin, a statistically significant reduction in tooth sensitivity (evaluated by a VAS) was observed compared to a placebo dentifrice ([Bizreh and Milly, 2022](#))

The ability for calcium-containing bioactive glasses when combined with the peroxide whitening agent to reduce tooth sensitivity whilst patients are undergoing tooth bleaching has been reviewed ([Favoreto et al., 2023](#)), concluding that there is a small but positive impact on these agents to reduce tooth sensitivity whilst patients are undergoing tooth bleaching. However, this review specifically excluded any analysis of studies with bioglass-containing dentifrices. The evidence specifically for NovaMin dentifrices is therefore minimal and thus, this study is required to investigate the potential for NovaMin to provide tooth sensitivity relief whilst patients are undergoing tooth bleaching.

The tooth sensitivity benefits of  $\text{KNO}_3$  containing dentifrices are well established ([Sharma et al., 2012](#), [Hu et al., 2018](#)). Additionally, there is clinical evidence to support the role of potassium ions at reducing tooth sensitivity while patients undergoing tooth bleaching. One study evaluated the twice-daily use of a 5%  $\text{KNO}_3$  dentifrice for 2 weeks before, and during a 14 day treatment with a 9.5% hydrogen peroxide gel compared to a standard dentifrice ([Haywood et al., 2005](#)). The study concluded that use of the potassium-containing dentifrice resulted in statistically significantly more sensitive-free days than the control dentifrice. Similar findings were found in another study ([Pierote et al., 2020](#)) where a variety of dentifrices were used during and after peroxide bleaching with a 26% hydrogen peroxide gel, concluding that dentifrices containing  $\text{KNO}_3$  and sodium fluoride were able to reduce tooth sensitivity during peroxide bleaching. The same study also evaluated tooth color finding that all of the tested dentifrices (including controls) lead to the same tooth color at 4 and 24 weeks after bleaching. A separate study by the same authors concluded that a potassium ion-containing dentifrice was effective at helping to reduce tooth sensitivity when applied via a tray for 4 hours per night during the bleaching period ([Pierote et al., 2019](#)). In a further study ([Adil et al., 2021](#)), use of a  $\text{KNO}_3$  / sodium monofluophosphate gel post bleaching was found to be effective at reduction of tooth sensitivity when a 35% hydrogen peroxide bleaching treatment was used. Tooth sensitivity relief while using a  $\text{KNO}_3$  dentifrice was also observed in a population with mild-to-moderate fluorosis following 35% hydrogen peroxide treatment ([Nanjundasetty and Ashrafulla, 2016](#)). Contrastingly, application of a  $\text{KNO}_3$  gel immediately prior to bleaching with hydrogen peroxide was not found to reduce tooth sensitivity but also did not adversely affect the whitening efficacy of the bleaching treatment ([de Lima et al., 2022](#)). Further, an unpublished study found that use of a 5%  $\text{KNO}_3$  dentifrice before, during and after a bleaching treatment lead to a non-statistically significant reduction in tooth sensitivity during the 7 days post treatment, although statistically significant fewer subjects reported tooth sensitivity compared to the control dentifrice [CCI](#) [REDACTED] A systematic review of tooth sensitivity associated with tooth bleaching, drawing on 13 publications, has concluded that 5%  $\text{KNO}_3$  is effective at reducing tooth sensitivity at least up to 24 hours post conclusion of the bleaching treatment ([Krishnakumar et al., 2022](#)).

## 2 STUDY OBJECTIVES AND ENDPOINTS

**Table 2-1 Study Objectives and Endpoints**

Objectives	Endpoints
Primary	
To characterize the subject-perceived sensitivity protection profile of a 5% NovaMin-containing dentifrice, a 5% KNO 3 -containing dentifrice and a reference fluoride dentifrice during and for 2 weeks post tooth bleaching.	
Daily responses from the tooth sensitivity questionnaire through the study in:-
 
 
• Visual analogue scale (VAS)
 
• Labelled Magnitude scales (Intensity, Duration, Tolerability, Description) - LMS
 
• Bothersomeness score – NRS
 
• Number of subjects who experience tooth sensitivity
 
• Number of subjects who used analgesics to alleviate tooth sensitivity
 

Secondary	
To investigate the ability of a 5% NovaMin-containing dentifrice to reduce self-perceived tooth sensitivity as measured by a subject-completed tooth sensitivity questionnaire compared to a 5% KNO 3 -containing dentifrice and a reference fluoride dentifrice during tooth bleaching.	
Responses from the tooth sensitivity questionnaire completed during tooth bleaching (Visit 2-3) in:-
 
 
• Mean VAS
 
• Mean LMS
 
• Mean Bothersomeness
 
• % tooth sensitivity-free days
 
• % days analgesics used to alleviate tooth sensitivity
 

To investigate the ability of a 5% NovaMin-containing dentifrice to reduce self-perceived tooth sensitivity as measured by a subject-completed tooth sensitivity questionnaire compared to a 5% KNO 3 -containing dentifrice and a reference fluoride dentifrice for 2 weeks from the end of tooth bleaching.	
Responses from the tooth sensitivity questionnaire completed during the 2 weeks post completion of tooth bleaching (Visit 3-4) in:-
 
 
• Mean VAS
 
• Mean LMS
 
• Mean Bothersomeness
 
• % tooth sensitivity-free days
 
• % days analgesics used to alleviate tooth sensitivity.
 

To confirm the tooth whitening efficacy of peroxide tooth bleaching with concurrent, twice daily use of a 5% NovaMin-containing dentifrice, a 5% KNO 3 -containing dentifrice and a reference fluoride dentifrice as measured by VITA Bleachedguide 3D Master.	Change in mean VITA shade score from pre- to post-tooth bleaching (Visit 2-3)
Exploratory	
To explore subject's oral-health related quality of life during peroxide tooth bleaching when simultaneously using either a 5% NovaMin-containing dentifrice, a 5% KNO 3 -containing dentifrice or a regular fluoride dentifrice.	Change from screening in responses from the Dentine Hypersensitivity Experience Questionnaire (DHEQ) during the tooth bleaching period (Visit 2-3) and for the two weeks post tooth bleaching (Visit 3-4)
To investigate the ability of a 5% NovaMin-containing dentifrice to reduce self-perceived tooth sensitivity as measured by a subject-completed tooth sensitivity questionnaire compared to a 5% KNO 3 -containing dentifrice and a reference dentifrice for 2 weeks from the	
Responses from the DHEQ and tooth sensitivity questionnaire during the tooth bleaching period (Visit 2-3) and separately for the 2 weeks post tooth bleaching (Visit 3-4) in:-
 
 
• Mean VAS
 

Property of Haleon- Confidential

May not be used, divulged, published or otherwise disclosed without the consent of Haleon

end of tooth bleaching separately for those subjects with and without clinically-confirmed dentine hypersensitivity (DH).	
 
• Mean LMS
 
• Mean Bothersomeness
 
• % tooth sensitivity-free days
 
• % days analgesics used to alleviate tooth sensitivity
 
• Change from screening in DHEQ
 

To explore subject's experience of peroxide tooth bleaching when simultaneously using either a 5% NovaMin-containing dentifrice, a 5% KNO 3 -containing dentifrice or a regular fluoride dentifrice.	Post-whitening questionnaire

No formal success criterion has been defined for this exploratory study; however, if the NovaMin dentifrice provides sensitivity protection during tooth bleaching, it would be expected that subject perceived tooth sensitivity (measured by the subject completed sensitivity questionnaires) for the NovaMin dentifrice would be directionally superior to the reference dentifrice during the study period.

### 3 STUDY DESIGN

This is a randomized, examiner blind, single-center, controlled, three arm, parallel group, proof-of-principal study to evaluate tooth sensitivity during and following a course of tooth bleaching in subjects with and without clinically-confirmed dentine hypersensitivity. The study will recruit generally healthy subjects who wish to undergo peroxide tooth bleaching. A schematic of the principal study assessments and procedures is provided in Fig 3-1.

Sufficient subjects will be screened to randomize approximately 90 subjects to study treatment (approximately 30 per treatment group).

Subjects will attend a Screening visit (Visit 1) where, having obtained their written informed consent, relevant details of their medical history, demography and current medications will be recorded. Subjects will then undergo oral soft tissue (OST) and oral hard tissue (OHT) examinations. The shade (color) of the facial surfaces of the anterior 6 maxillary and mandibular teeth (tooth numbers 6-11 and 22-27) will then be assessed clinically using the VITA Bleachedguide 3D-MASTER ([Gómez - Polo et al., 2015](#)).

Those subjects with a self-reported history of dentine hypersensitivity (DH) will be clinically-evaluated to confirm their DH status [Y/N] (including Erosion/Abrasion/Recession (EAR) assessment, gingival assessment, tooth mobility assessment and evaporative (air) sensitivity assessment (Schiff Sensitivity score)).

[figure not shown]
Subjects meeting all study criteria will be considered as eligible to proceed and will complete the tooth sensitivity questionnaire and the DHEQ-15 after being trained in the correct usage of these questionnaires. Eligible subjects will then be stratified (based upon their DH status [Y/N]) and randomized to treatment group. Subjects will then be dispensed their allocated dentifrice, timer and toothbrush and will undergo a supervised brushing with their allocated dentifrice at the clinical site and scheduled to attend visit 2 (2 weeks ± 2 days after Screening). Subjects will be instructed to use their assigned dentifrice twice daily (morning and evening) for 1 timed minute.

At Visit 2, subjects will undergo a review of their current medications and compliance to treatment and will then undergo an OST examination. The shade (color) of the facial surfaces of the anterior 6 maxillary and mandibular teeth (tooth numbers 6-11 and 22-27) will then be assessed in the same way as at Visit 1.

Property of Haleon- Confidential

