### **5 STUDY PROCEDURES**

All study procedures for each visit and the order in which they should be performed (where practically feasible) should be completed in accordance with [Table 5-1 Schedule of Activities](#).

Adherence to the study design requirements, including all procedures are essential and required for study conduct. All procedures will be conducted by the Investigator (or suitably qualified designee) and all information and data collected will be documented in the CRF. Clinical examiner(s) involved in the screening, safety and efficacy assessments will be appropriately qualified dental professionals, registered to practice in Canada.

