3. The tooth sensitivity questionnaire will evaluate overall tooth sensitivity with LMS and VAS assessments. The questionnaire will be completed for the duration of tooth bleaching treatment and for 2 weeks post completion of tooth bleaching.
4. The supplied tooth bleaching kit will be used once under supervision at the study site and then once per day at home (for a total of 7 days) in accordance with the manufacturer's instructions.
5. Female subjects of child-bearing potential only.
6. DH assessments to be administered only to subjects with self-diagnosed DH.
7. Stratification will be based on clinically-diagnosed DH (Y/N) at screening.
8. Sections 1&2 to be completed at V2. Section 1 (questions 7-9 only) and Section 2 to be completed at V3&4. DHEQ to be completed at the study site.

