#### 6.2.1.4 Evaporative (Air) Sensitivity Assessment (Schiff sensitivity score)

The Evaporative (air) Sensitivity Assessment will be assessed for teeth that will be peroxide bleached and that exhibit none of the dentition exclusion criteria for tooth DH, which show signs of EAR, which have an MGI=0 directly adjacent to the exposed dentine and which have clinical mobility = 0 only.

Property of Haleon- Confidential

May not be used, divulged, published or otherwise disclosed without the consent of Haleon

The examiner will apply an evaporative air stimulus by directing a maximum one second application of air from a dental air syringe to the exposed dentine surface from a distance of approximately 1 cm. The subject response will be scored using the Schiff Sensitivity scale immediately following the evaporative air stimulus. The Schiff Sensitivity scale is an examiner based index ([Schiff et al., 1994](#)) focusing on a combination of specific, observable, physical, behavioral and verbal responses from the subject as a result of the stimulation of exposed dentine, rather than solely an oral request from the subject to discontinue stimulation and may facilitate discrimination. The examiner will indicate the subject's response to the evaporative air stimulus, after the stimulation of each individual tooth, using the Schiff Sensitivity scale as below.

Score	Subject Response
0	Subject does not respond to air stimulation
1	Subject responds to air stimulus but does not request discontinuation of stimulus
2	Subject responds to air stimulus and requests discontinuation or moves from stimulus
3	Subject responds to stimulus, considers stimulus to be painful, and requests discontinuation of the stimulus

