### 8.3.2 Secondary Endpoint Analyses

The VAS score for tooth sensitivity for the first 7 days during the tooth bleaching period will be analyzed using a Mixed Model with Repeated Measures (MMRM), with study product, DH diagnosis at screening (yes/no), days of bleaching and study product by days of bleaching interaction as fixed effects. The VAS score at screening will also be included as a covariate. Subject will be included as a repeated measure with compound symmetry covariance structure. Kenward Rogers degrees of freedom approach will be applied ([Kenward and Roger, 1997](#)). The overall (across all days) least square means (with SE and 95% confidence intervals [CI]) for each study product will be presented along with the difference (with SE and 95% CI).

A separate MMRM will be applied to evaluate the pairwise differences between products for each day. This will be identical to the above MMRM but subject will be included as a repeated measure with unstructured covariance matrix. In case of convergence issues, the Toeplitz, Autoregressive (1), Compound Symmetry covariance structures will be applied until convergence is attained (all heterogeneous versions first and then the same sequence of homogeneous versions). The least square means (with SE and 95% CI) for each study product will be presented along with the pairwise differences (with SE and 95% CI) between products for each day using the appropriate contrasts from the MMRM results.

As a further sensitivity analysis, the mean VAS score for tooth sensitivity over the tooth-bleaching period (Visit 2 [at home] to Visit 3) for a subject will be analyzed using an Analysis of Covariance (ANCOVA) model will be used with study product and DH diagnosis at screening (yes/no) as fixed effects and the VAS score at screening as a covariate. The least square means (with SE and 95% CI) for each study product will be presented along with the difference (with SE and 95% CI).

The LMS and the Bothersomeness scores during the tooth-bleaching period will be analyzed and presented in identical fashion to the VAS scores endpoint using the same MMRMs and ANCOVA (replacing the respective screening result as a covariate).

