**When completing this form please consider your experience over the last 24 hours**

Have your teeth been sensitive ? Y/N     **If NO do not complete any further questions.**

Please make a single vertical mark at the point on the line which represents the degree of overall tooth sensitivity (eg twinges, pain and other sensations in your teeth) that you have experienced **over the last 24 hours**

[figure not shown]
No Sensitivity	_____	Extreme Sensitivity
-------------------	-------	------------------------

For Site use only: \_\_\_\_\_ mm     \_\_\_\_\_ Initials

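### At Visit 1 the 24-hour sensitivity questionnaire follows the air test, so provoked sensitivity can enter the screening scores, mainly in DH-positive subjects; arm comparisons stay unbiased

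*Combined protocol and SAP*

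**What the plan says.** **Order.** Section 3 describes the DH evaluation with the Schiff air test, then says "Subjects meeting all study criteria will be considered as eligible to proceed and will complete the tooth sensitivity questionnaire and the DHEQ-15", and then moves to stratification and randomization. Table 5-1 lists the DH assessments above both questionnaires. Section 5 makes the order of that table operative, in a sentence that ends by naming it: "All study procedures for each visit and the order in which they should be performed (where practically feasible) should be completed in accordance with".

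**Who receives air.** Table 5-1, footnote 6: "DH assessments to be administered only to subjects with self-diagnosed DH". Section 6.2.1.4 narrows this to teeth that will be bleached, have no tooth-level exclusion, show erosion, abrasion or recession, and "which have an MGI=0 directly adjacent to the exposed dentine and which have clinical mobility = 0 only".

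**What a positive response is.** Schiff 2 reads "Subject responds to air stimulus and requests discontinuation or moves from stimulus". Schiff 3 adds that the subject finds the stimulus painful. Section 6.2.1 requires a score of 2 or more on at least one qualifying tooth for a DH diagnosis. Footnote 7: "Stratification will be based on clinically-diagnosed DH (Y/N) at screening".

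**What the form asks.** Section 9.10: "When completing this form please consider your experience over the last 24 hours". It opens with a Yes/No question, and a No ends the form.

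**How the score is used.** Section 8.3.1 summarizes each primary endpoint at Screening, at Visit 2 before bleaching, and daily. Section 8.3.2 says of the VAS model "The VAS score at screening will also be included as a covariate", and treats LMS and bothersomeness alike with their own screening scores.

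**The concern.** A DH-positive subject has, by definition, just asked for an air stimulus to stop, moved away from it, or found it painful. Later in the same visit the subject reports sensitivity over a window that contains that event. Someone with no spontaneous sensitivity could truthfully answer Yes because of the test and go on to complete the VAS, LMS and bothersomeness scales. Subjects without self-reported DH get no such stimulus, and Table 5-1 schedules no air test at Visits 2, 3 or 4. Screening scores are thus collected under different conditions from later scores, and under different conditions in different subjects.

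Two uses of the score are exposed. The first is descriptive. An inflated Screening value produces a fall to Visit 2 in every arm, including the reference. Section 8.3.2 itself expects the dentifrice to affect Visit 2 sensitivity, so a reader could take such a fall as two weeks of product benefit. Randomization does not protect a within-arm comparison, nor a comparison of DH-positive with DH-negative baselines. The second is precision. The screening score is the only baseline score in the VAS, LMS and bothersomeness models, because Section 8.3.2 deliberately leaves Visit 2 out, and a noisier covariate explains less of the outcome.

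**Working it through.** The plan gives no figure for the effect of the air test, and Section 8.1 reports no formal sample size calculation, so there is no stated figure to reproduce. The order of procedures can be read directly. The sizes below rest on assumptions.

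**1. Who is affected.** About 90 subjects are randomized, 30 per arm, with 40-50% DH-positive (Sections 4.1 and 7.3).
- DH-positive in total: 0.40 × 90 = 36 to 0.50 × 90 = 45.
- Per arm: 0.40 × 30 = 12 to 0.50 × 30 = 15.

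A Schiff score of 2 or more on a tested tooth makes the subject DH-positive. A tested subject whose teeth all score 0 or 1 is DH-negative. A self-reporter with no qualifying tooth receives no air.

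**2. Descriptive shift.** If air raises the screening VAS of DH-positive subjects by a mean of *d* mm, their change from Screening is lowered by *d*, and the pooled change by (DH share) × *d*. With *d* = 5 to 15 mm (assumed):
- DH-positive stratum: a spurious fall of 5 to 15 mm.
- All subjects: 0.40 × 5 = 2.0 mm to 0.50 × 15 = 7.5 mm, alike in all three arms.

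**3. Product comparison.** ANCOVA was simulated with 3 arms of 30, 13 DH-positive per arm, and terms for product, DH status and screening score. Assumed values: SD 20 mm, baseline-outcome correlation 0.6, true effect −8 mm in one arm, and an air-provoked add-on to the screening score in DH-positive subjects only (4,000 runs per row).

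| Add-on mean / SD (mm) | Estimated difference (mm) | Model SE (mm) | SE ratio | DH-positive change from Screening (mm) |
|---|---|---|---|---|
| 0 / 0 | −8.16 | 4.14 | 1 | −2.74 |
| 10 / 0 | −8.01 | 4.15 | 4.15/4.14 = 1.00 | −12.61 |
| 20 / 0 | −8.01 | 4.14 | 4.14/4.14 = 1.00 | −22.66 |
| 10 / 10 | −8.01 | 4.26 | 4.26/4.14 = 1.03 | −12.68 |
| 20 / 20 | −7.87 | 4.48 | 4.48/4.14 = 1.08 | −22.69 |

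The estimates scatter around −8; a longer run of 40,000 replicates gave −7.99 to −8.00 in every row. The DH term absorbs a constant add-on, so only its variability costs precision. The change from Screening moves one-for-one with the add-on. The uncontaminated value is the arm effect averaged over three arms, −8/3 = −2.67.

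**4. Range for precision.** Reliability is the share of the DH-positive screening variance, within that stratum, that is not test noise. Noise SD 10 gives 400/(400 + 100) = 0.8; noise SD 20 gives 400/(400 + 400) = 0.5. A second simulation (90 subjects, 45% DH-positive) gave these SE ratios:

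| Reliability (assumed) | Correlation 0.4 | 0.5 | 0.6 |
|---|---|---|---|
| 0.8 | 1.006 | 1.016 | 1.026 |
| 0.5 | 1.028 | 1.049 | 1.083 |

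The two simulations agree where they overlap (1.03 against 1.026; 1.08 against 1.083). Both use a single outcome per subject, so they approximate the planned repeated-measures model.

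**The case against.** The strongest reply is that nothing the plan sets out to compare is biased. Screening precedes randomization, allocation is stratified by DH status, and the VAS, LMS and bothersomeness models carry a DH term. Those endpoints are levels during and after bleaching, not changes from Screening. The only stated expectation (Section 2) is that NovaMin be directionally better than the reference, and a fall shared by all arms cannot produce that. The negative binomial models use no screening score, so a flipped Yes/No answer at Screening does not enter them. All of this stands, and it confines the point to descriptive Screening values and precision.

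Three stronger readings are tempting but unsupported:
- **That only the DH stratum is touched.** Testing follows self-report while stratification follows diagnosis, so tested subjects scoring 0 or 1 join the DH-negative stratum. Strong responses are concentrated in DH-positive subjects; exposure to air is not exclusive to them.
- **That every tooth with exposed dentine receives air.** Section 6.2.1.4 restricts it further.
- **That the DHEQ baseline is spoiled.** Section 8.3.3 analyses total and domain scores. The domains are built from Section 2 of the DHEQ (Section 6.3.3), which asks about daily life over the last week. A stimulus of at most one second has little route into those items. The Section 1 intensity and tolerability ratings are more exposed.

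It can also be said that giving the forms only to eligible subjects is a reasonable choice. It is, and the order can be changed without giving it up.

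**Conclusion.** The point holds in limited form. The documented order places the 24-hour questionnaire after the air test, with no instruction to set the test aside, so provoked sensitivity can inflate the screening VAS, LMS, bothersomeness and Yes/No answers or add noise to them, mainly in the 36 to 45 DH-positive subjects. Screening versus Visit 2 within arms, and DH-positive versus DH-negative baselines, should not be read at face value.

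A reader might infer that the product comparisons are compromised. They are not: the expected bias is zero, and the cost is an SE increase of about 1-8%. The upper end needs half of the DH-positive screening variance to be test noise; at reliability 0.8 the increase is about 1-3%. Neither these noise levels nor the 5-15 mm shift comes from the documents, and the true effect could be close to zero. This is a cheap improvement to a baseline measurement, not a threat to the trial's conclusions.

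**What to change.** In Table 5-1 and Section 3, move the DH assessments, or at least the air test, to after the eligibility review and the Visit 1 questionnaires and before stratification and randomization. State that the questionnaires are completed before any air stimulus.

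This is feasible because DH status is not among the inclusion or exclusion criteria (Sections 4.2 and 4.3); it sets the stratum and the 40-50% quota. The new order keeps the forms limited to eligible subjects, as Section 6.3.3 requires for the DHEQ, and keeps the DH assessments before randomization, as Section 6.2.1 requires.

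The cost is a reordered table and one edited paragraph. DH status is known slightly later in the visit, so a subject not needed for the quota may already have completed the forms. If the order cannot change, a sentence telling subjects to disregard sensations caused by the examination would help. If enrolment has begun, the report should state the order used and caution against interpreting change from Screening to Visit 2 in DH-positive subjects.
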